6.2 Schedule of Assessments

Table 6.1 Schedule of Assessments

CIP Number 2023-A00150-45 Final version 0.2

CONFIDENTIAL May 2023

			Primary Inter	vention Period		Long Term Intervention Period			
Visit	Screening ¹	Baseline ²	Visit 1	Visit 2	Visit 3	Visit 1.2	Visit 2.2	Visit 4	End of Study Visit
Timepoint	Day 1	Day 1	Week 4	Week 8	Week 12	Week 16	Week 20	Week 24	Week 26
Visit Window	NA	NA	\pm 7 days	\pm 7 days	\pm 7 days	\pm 7 days	\pm 7 days	\pm 7 days	\pm 7 days
Assessments	In-Clinic + Remote	In-Clinic	Remote	Remote	In-Clinic	Remote	Remote	In-Clinic	Remote
						patients	who switch		
ICF	•								
Eligibility Check	•								
Modified Hoehn and Yahr staging	•							•	
MoCA	•								
Medical History & Demographics		•							
Randomisation	•								
Prior Rehabilitation History	•								
Prior- and Concomitant Medication	•			-	•				
6MWT ³		•			•			•	
Ecological remote gait data collection		for 2 weeks after BL			for 2 weeks after V3			for 2 weeks after V4	
Mini-BESTest		•			•			•	
MDS-UPDRS		•			•			•	

CIP Number 2023-A00150-45 Final version 0.2

CONFIDENTIAL May 2023

FOG-Q	•			•			•	
PDSS-2	•	•	•	•	•	•	•	
Pain VAS	•	•	•	•	•	•	•	
PDQ-39	•			•			•	
PDQ-8		•	•		•	•		
CGI-S / PGI-S	•							
CGI-I / PGI-I				•			•	
Satisfaction Questionnaire	•			•			•	
Falls diary								
Conventional Physiotherapy tracking		From ICF to EOS						
AEs								
Adherence				•			•	

ICF: Informed Consent Form; 6MWT: 6 Minutes Walk Test; Mini-BESTest: Mini Balance Evaluation Systems Test; MOCA: Montreal Cognitive Assessment; AEs: Adverse Events; FOG-Q: Freezing of Gait Questionnaire; MDS-UPDRS I, II & III: Unified Parkinson's Disease Rating Scale parts I, II and III; PDQ-39: Parkinson Disease Questionnaire; PDQ-8: Parkinson Disease Questionnaire Short Form; CGI-S/PGI-S: Clinical/Patient Global Impression of Severity; CGI-I/PGI-I: Clinical/Patient Global Impression of Improvement; PDSS-2: Parkinson Disease Sleep Scale 2;

¹A reflection period of fifteen to thirty days must be given to the subject to decide upon their participation.

² BL assessments will take place right after the Screening Visit.

³ Patients on the FeetMe arm will perform weekly 6MWTs as part of their rehabilitation program using the FeetMe Rehabilitation application.

Note: Visit windows are to be calculated compared to the original schedule, not the previous visit

6.3 Study Population

6.3.1 Sample Size

A total of 150 patients will be recruited for this study. A drop-out percentage of 20% was inferred from previous studies using FeetMe Rehabilitation application on a similar population and was considered in the calculation of the sample size.

6.3.2 Inclusion Criteria

All patients must fulfil the following criteria:

- 1. Written informed consent to participate in the study.
- 2. Male or female patients between 40 to 70 years of age, inclusive.
- 3. Body weight range of 40 kg to120 kg and a body mass index (BMI) of 18 to 34 kg/m2.
- 4. Diagnosis of Idiopathic Parkinson's disease (PD) according to UK Brain Bank Criteria (2/3 symptoms), with Hoehn and Yahr (H&Y) staging level 2, 2.5 or 3.
- 5. Disease onset of at least 3 years prior to enrolment.
- 6. Patients with a history of 50% levodopa responsiveness based on motor signs.
- 7. On stable treatment of PD medication for at least 30 days before screening and with no expected major changes during the first 3 months of the study.
- 8. Prescription for physiotherapy available.
- 9. Ability to walk without aid for at least 6 minutes.
- 10. Shoe size between 35 46 (European Standard).
- 11. Intact skin on feet.
- 12. Adequate visual and auditory acuity to perform the rehabilitation program and the assessments in the Investigator's judgement.
- 13. Comfortable with the use of a smartphone. If assistance is required for the use of FeetMe technology, a caregiver or volunteer is fully available to assist the patient.
- 14. Willingness to be regularly contacted via phone-calls.
- 15. Willingness to suspend conventional physiotherapy treatment and start the FeetMe rehabilitation program, if applicable.
- 16. French speaker.

6.3.3 Exclusion Criteria

Patients must not fulfil the following criteria:

- 1. Medical history indicating a Parkinsonian syndrome other than idiopathic PD.
- 2. Unable to walk without walking aid or presence of an injury preventing the patient to walk.
- 3. Any relevant comorbidity or vestibular/visual dysfunctions limiting locomotion or balance.
- 4. Clinically significant comorbidities which in the judgement of the investigator may preclude the reliable gait assessment of the patient.
- 5. Patients with poor wound healing or broken skin on the feet.
- 6. Patients with foot implants.

- 7. Montreal Cognitive Assessment (MoCA) score $\leq 24/30$.
- 8. Patients with dementia.
- 9. Patients with apathy.
- 10. Participation in another clinical trial with an investigational drug/ therapeutic within the three months before screening and during the study, unless agreed by the Sponsor.
- 11. Patients who had Lee Silverman Voice Treatment (LSVT) Big therapy within the past 12 months or have it planned during the course of the study.
- 12. Patients with Deep Brain Stimulation planned during the first 12 weeks of the study.
- 13. Patients with pacemakers.
- 14. Patients performing vigorous exercise > three times a week, 30 mins or more per session

6.3.4 Patient Replacement

Patients will not be replaced in the study.

6.4 Investigational Medical Device

6.4.1 Device Description

FeetMe® Monitor connected insoles is a wearable medical device that measure spatio-temporal gait parameters and plantar pressure to support the mobility assessment of individuals. The hardware product consists of two regular shape insoles and a double-head wireless charger with wall adaptor to charge both insoles simultaneously. The insoles are available in 12 sizes ranging from 35 to 46 (EU standard) or from 4.5 to 13 (US standard for men) or 5.5 to 14 (US standard for women).

An insole includes one Inertial Measurement Unit (IMU) with a 3-D accelerometer and a 3-D gyroscope to capture movement in 6 directions and eighteen capacitive cell pressure sensors, around 15 mm² cell area each. In the insoles heel strike (HS) and toe off (TO) events are detected by the pressure sensors and the related temporal parameters are calculated from HS and TO event timings. HS, TO and stride length are calculated in each insole and are defined as insole-based parameters. For each insole, these parameters are sent to a mobile application via Bluetooth Low Energy. The velocity, stride length, stride duration, stance duration, swing duration, step duration, single support duration and double support durations, cadence, number of steps, distance, duration of walking test are defined as mobile-based parameters and are calculated by a dedicated mobile application. The mobile application allows the real-time recording and/or visualization of the gait parameters. FeetMe® Monitor is marketed, CE-marked class Im medical devices (under rule 1 and under rule 12 of ANNEX IX of Medical Device Directive 93/42/EEC amended by Directive 2007/47/EC) (MDD), and FDA approved (510k exempt)). Insoles are manufactured by FeetMe.

Figure 4. Picture of a FeetMe Insole with charger and related smartphone application

Page 34 of 117

The individual chargers are to be connected to a power outlet and positioned on the white round marks of the insoles. The induction chargers will position themselves automatically. LED lights will indicate the charging status of the insoles. It takes approximately 2.5 hours for a complete charge of the insoles.

Detailed user guides will be provided for both the patients and investigators on each device.

For further information please refer to the Investigator's Brochure.

6.4.2 Data collection

Data collected by the insoles are described below.

Unipedal parameters collected

- Stride duration (ms)
- Stance duration (ms)
- Swing duration (ms)
- Stride length (m)
- Stride elevation (m)
- Velocity (m/s)
- Swing velocity (m/s)
- Cadence (steps/min)

Bipedal parameters collected

- Single support duration (ms)
- Double support duration (ms)
- Step duration (ms)

Balance data and pressure data

- Mean CAPA values during stance phase for each sensor
- Extraction of 16 points of the estimated center of pressure (COP) trajectory during stance phase
- antero-posterior & medio-lateral COP trajectories: amplitude of COP
- Center of pressure trajectory
- ground force reaction (heel & toe)

Exercises data

- percentage of success of exercise
- daily/weekly/monthly practiced time
- practiced time per exercise
- daily/weekly/monthly number of exercises performed

All personal data collected for the patient follow-up (name,phone number, email adress) will be deleted at the end of the study.

6.4.3 Packaging and Labelling

Each pair of insoles will be packed individually along with chargers and will be identified with a unique serial number. The sites will be supplied with multiple pairs in each size. Each patient will receive one pair of insoles and the charger. A mobile device with the FeetMe Rehabilitation application will be provided to the patients in the FeetMe rehabilitation program and patients in the Conventional physiotherapy arm who don't have Android devices. Additionally, each site will receive a mobile device with the FeetMe Evaluation application installed on it to perform on-site gait analysis, in case necessary (e.g.: a patient forgets to bring their device to a visit). No study specific labelling will be used.

6.4.4 Blinding

Blinding is not applicable (see Section 6.1).

6.4.5 Supply and Accountability

The devices (insoles, chargers, mobile devices) will be supplied by FeetMe. It is not allowed to use the devices for other uses than those defined in the clinical investigational plan. Devices must be exclusively used for the identified patients of this study.

The Investigator or designee must confirm the receipt of the devices. Upon receipt of the devices the Investigator or designee will conduct an inventory of supplies, verify and document that the devices are intact and the correct amount have been shipped. The CRA must verify the documentation. Request of new insoles (e.g.: due to higher need of a particular size) or exchange of faulty ones will be ensured by the Sponsor. The site must keep track of the return of any equipment.

At the end of the study all devices will need to be returned to the Sponsor in their original packaging.

Further details are provided in the Study Procedure Manual.
7 STUDY ASSESSMENTS BY VISIT

7.1 Introduction and reflection period

During their routinely scheduled visit at the investigational site patients who express interest in participating in the study will be introduced to the device. Then, patients return to their home and have a reflection period of 15 days to 1 month. If judged to be comfortable with and interested in the technology they will screened for participation. Beforehand the inclusion / exclusion criteria will be assessed at high level without capturing any data to make sure there are no obvious exclusionary factors. The MoCA and no other only protocol mandated assessment will not be performed.

7.2 Screening

7.2.1.1 Screening

If the patients deciced during the reflection period to participate they will return to the site for the Screening Visit.

The following assessments will take place within the Screening Visit done by the investigators (neurologists):

- Verify the informed consent.
- Eligibility criteria evaluation, including the definition of disease stage (H&Y) and cognitive status (MoCA), dementia and apathy.

All inclusion and exclusion criteria will be assessed to confirm the patient's eligibility for the study. Study sites are required to document all screened patients initially considered for inclusion in the study and collect the reason of screening failure. For the evaluation of dementia and apathy there are no protocol mandated assessments, the sites can use their routine diagnostic tools.

• Rehabilitation history

7.2.1.2 Randomisation

Eligible patients will be randomised using an Interactive Voice/Web Response System (IXRS) randomised either on the conventional physiotherapy or on the FeetMe arm in a 1:1 ratio. Randomisation will be stratified by the covariable "already in a rehabilitation program" and by study site. We will use a dynamic randomisation procedure by minimization using the Pocock and Simon method. Randomization will result in the assignement of the unique Patient ID, which will be used on all study-related documents pertaining to the patient. Any identification numbers that are assigned will not be reused even if the patient does not continue in the study.

7.2.2 Re-Screening

Patients who fail screening criteria can be retested once according to the Investigator's judgement. In this case, the same ID previously assigned will be used in the study.

7.2.3 Screen Failure

Patients who do not meet the eligibility criteria will be considered screen failed. The reason for screen failure must as a minimum be documented.

7.3 Baseline Visit

All randomised patients will participate in the Baseline Visit. This visit will be on the same day as the Screening Visit.

Patients will be instructed in the use of the FeetMe Monitor and wear the insoles for the duration of the visit, while performing a series of assessments.

The following assessments will be performed at the Baseline Visit:

CIP Number 2023-A00150-45 Final version 0.2

- Demographic data collection (month and year of birth; gender, weight, height, leg length, shoe size)
- Recording of relevant medical history, prior medications
- Gait Assessments, which must be performed in ON-phase:
 - 6 Minutes Walk Tests (6MWT)
 - Mini-BESTest

During the 6MWT and the Mini-BEST gait data will be recorded using the FeetMe Rehabilitation or Evaluation application. Specific instructions set out in the Site User Manual must be followed when setting up and executing the assessments.

- Disease specific rating scales:
 - The Movement Disorder Society sponsored Revision of the Unified Parkinson's Disease Rating Scale (MDS-UPDRS)
- Other Assessments:
 - Freezing of Gait Questionnaire (FOG-Q)
 - Parkinson Disease Sleep Scale 2 (PDSS2)
 - Pain VAS
 - Parkinson Disease Questionnaire (PDQ39)
 - Patient Global Impression of Severity (PGI-S)
 - Clinical Global Impression of Severity (CGI-S)

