	During their routinely scheduled visit at the investigational site patients who express interest in participating in the study will be introduced to the device. If judged to be comfortable with and interested in the technology, patients will return to their home to consider their participation. There is a reflexion period that lasts at least fifteen days up to one month If the patient decides to participate in the study, they return to the site for the screening visit. Once the informed consent is signed the screening assessments will be performed by the investigator (the neurologist). If eligible, the patients will be randomised either into the conventional physiotherapy (CPt control group) or the FeetMe rehabilitation program (experimental group).
	Primary Intervention Period
	Once randomised patients will proceed to the Baseline Visit (BL). At the BL visit, all participants (experimental and CPt control group) will be trained to use the FeetMe devices and will wear the insoles as much as possible throughout the visit. Standard gait and balance assessments will be performed (6 minute walk test (6MWT), MiniBESTest). Additionally, patients will perform multiple clinical assessments designed to assess: disease severity, gait, balance, mobility, etc. by completing different surveys.
	Following the BL visit, all patients will enter an initial 12 week period according to their patient group. Every patient in the study will be provided with a pair of insoles and will take the device to their homes. All patients, whatever the group of randomisation, will be asked to wear them as much as possible for 14 days after the BL visit to allow continuous gait data collection. This will permit the gathering of extensive data on a considerable number of gait parameters in a more familiar and natural setting reflecting real-life conditions. The FeetMe

patients will then continue to use the insoles according to the FeetMe rehabilitation program schedule.						
During the Primary Intervention Period (PIP), all patients will participate in two remote visits: Visit 1 (four weeks after BL) and Visit 2 (eight weeks after BL). During these visits, all patients will perform a short battery of self-reported questionnaires.						

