6 INVESTIGATIONAL PLAN

6.1 Study design and rationale

This is a multicentre, controlled, randomised in two parallel groups, open label study. The study will enroll 150 patients over approximately 18 months and 6 investigational sites.

Having multiple centres enrolling patients will not only maximise the capacity of recruitment but will allow for the evaluation of differences represented by geographical imbalances in the physiotherapy practices across France.

Patients who are found eligible and consent to participate will be randomised either on the conventional physiotherapy or on the FeetMe arm in a 1:1 ratio. Due to the set-up of the FeetMe program (i.e.: personal follow-up of the patients by an APA and the difference in the device needs between the two groups) and the obvious difference in the treatments, a blinded design is not possible. Nevertheless, the objective nature of the primary and main secondary endpoints measured by digital technology and the patient reported nature of most of the remaining outcome measures minimise any potential biassing effect originating from the open label design. Additionally, the final analysis will be performed by a independent blinded statistician.

The equal allocation of patients is maintained during the Primary Intervention Period (from the Baseline Visit till Visit 3) up to the primary endpoint evaluation at Week 12. It is in line with the duration of the FeetMe rehabilitation program. The program is built based on several regulatory recommendation including the HAS and the WHO and expert opinions suggesting that rehabilitation trainings typically show benefit after ten weeks. Additionally, most of the published data supports this duration together with the list of interventions analysed in the European Physiotherapy Guideline for Parkinson's Disease (Keus et al, 2014) where the median duration of the programs is eight weeks. The timing of the primary endpoint at Week 12 is adopted to this standard duration of an intensive rehabilitation therapy off approximately 3 months.

After the Primary Intervention Period patients will be offered to chose how to proceed i.e.: to continue on their original allocation, to switch arms or to stop treatment. In any case the patients will remain in the study until the week 26 EOS visit. The number of patients on the arms at this point will not be controlled and the data gathered will be exploratory in nature. This design is expected to:

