7.4 Primary Intervention Period

Following the Baseline Visit, all patients will begin their 12-week physiotherapy (or no-physiotherapy) regimen according to their randomisation.

During this period:

- All patients will participate in the Remote Gait Monitoring 1 and Visits 1-3 (Sections 7.3.1, 7.3.2, 7.3.3).
- Patients on the Conventional Physiotherapy arm, if they have access to it will start or continue their conventional physiotherapy and will keep track of it using the Conventional Physiotherapy Tracking Sheet (Appendix F). Patients who did not have access to CPt at the time of inclusion but manage to arrange one during the Primary Intervention Period will restart their PIP.
- On the other arm patients will start the FeetMe rehabilitation program (Section 4.4, Appendix A and B).
- In addition, all patients will keep a falls diary (Appendix G).

7.4.1 Remote Gait Monitoring 1

At the end of the Baseline Visit, all patients will take the FeetMe Insoles, mobile devices and chargers with them to their homes. A Patient User Guide will be provided.

- All patients will use the insoles remotely while performing their day-to-day activities (including physiotherapy) for two weeks. Data will be recorded in standalone mode (without a phone).
- Patients will download the data from the insoles at the end of each day.

7.4.2 Visits 1 and 2

Four and eight weeks after Baseline Visit, two remote visits (Visit 1 and 2) will take place. Patients will be asked to fill in the following questionnaires:

- PDSS-2
- Pain VAS
- Parkinson Disease Questionnaire, Short Form (PDQ-8).

7.4.3 Visit 3

Twelve weeks after Baseline Visit, that is, at the end of the 12-week Primary Intervention Period, all patients will participate in an in-clinic visit (Visit 3), where they will perform the same series of assessments as in the Baseline Visit. Patients will need to bring their FeetMe devices, their diaries, trackers and filled-in questionnaires to the visit.

The following assessments will be performed at Visit 3:

- Gait Assessments, which must be performed in the ON-phase:
 - 6 Minutes Walk Tests (6MWT)
 - Mini-BESTest.

During the 6MWT and the Mini-BESTest patients must wear the insoles. Specific instructions set out in the Site User Manual must be followed when setting up and executing the assessments.

- Disease specific rating scales:
 - MDS-UPDRS
- Other Assessments:
 - FOG-Q
 - PDSS2
 - Pain VAS
 - PDQ39

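### Open-label randomisation precedes the baseline walk and scales, so the baseline values in the Week 12 change analyses are not protected from knowledge of the arm

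*Protocol*

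**What the plan says.** The protocol gives the order of steps in four places, and they agree.

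- Section 7.2.1.2 places randomisation within Screening, and the Schedule of Assessments (section 6.2) marks it in the Screening column.
- The synopsis has patients go on to the Baseline Visit once they are randomised.
- Section 7.3: "All randomised patients will participate in the Baseline Visit. This visit will be on the same day as the Screening Visit".
- Section 6.2, footnote 2: "BL assessments will take place right after the Screening Visit".

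The 6MWT, Mini-BESTest, MDS-UPDRS, PDQ-39 and the other baseline scales are all listed in section 7.3, after randomisation.

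The trial is open label. Section 6.1 says that, given "the obvious difference in the treatments, a blinded design is not possible", and section 6.4.4 says blinding does not apply. Section 6.1 offers three mitigations: "the objective nature of the primary and main secondary endpoints measured by digital technology", the patient-reported nature of most other outcomes, and a blinded independent statistician.

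Treatment starts later. Section 7.4: "Following the Baseline Visit, all patients will begin their 12-week physiotherapy (or no-physiotherapy) regimen according to their randomisation". Section 7.4.1: "At the end of the Baseline Visit, all patients will take the FeetMe Insoles, mobile devices and chargers with them to their homes".

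**The concern.** The baseline is pre-treatment but post-allocation. No section delays release of the allocation or names an assessor who does not know the arm. Allocation may matter to a patient: those sent to FeetMe must be willing to suspend conventional physiotherapy (inclusion criterion 15), while some controls may have no physiotherapy at all (section 4.5).

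The mitigations in section 6.1 do not reach this point.

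- **Gait measures.** Insoles remove reading error, but the patient sets the pace. Section 8.1.1 asks for a comfortable pace and also for the greatest possible distance. Stance time variability and swing asymmetry come from the same self-paced walk.
- **Scales.** The investigator scores the Mini-BESTest (8.1.3), MDS-UPDRS Part III is clinician-rated (8.6.3) and PDQ-39 is self-reported (8.6.4).
- **Statistician.** Blinding at analysis does not change how the baseline data were collected.

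Baseline enters the primary, the key secondary and every secondary endpoint except the rate of falls. Section 9.5.1 constrains the two baseline means to be equal and justifies this by randomisation. That justification holds only if allocation cannot influence the baseline. The rank-based fallback also adjusts for baseline, so it gives no protection.

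A second consequence concerns the Full Analysis Set (section 9.1), which requires a baseline gait measurement. Under the present order that is a post-randomisation condition: a patient who leaves on learning the arm, before walking, drops out of the efficacy set.

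**Working it through.** **The protocol's own figure.** Section 9.4 gives a difference of 14 cm/s, an SD of 27 cm/s, correlation 0.5, two-sided alpha 0.05, power 80% and 20% dropout.

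- SD of change: √(2 × 27² × (1 − 0.5)) = 27.
- n per arm, normal approximation: 2 × (1.960 + 0.842)² × 27² / 14² = 58.4, so 59. The t-test solution is 59.4, so 60, with power 80.4%.
- With dropout: 60 / 0.80 = 75.

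The stated 60 and 75 per arm reproduce. This point does not alter them.

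**How a baseline shift reaches the estimate.** With two visits and complete data, the cLDA and ANCOVA estimates have the form

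(Week 12 difference) − ρ × (baseline difference),

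when the SDs are equal at both visits. Let d be an arm-related shift (FeetMe minus control) in the baseline only. The bias is −ρd, of size ρ|d|. An unadjusted change score would carry the whole of d.

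**Illustration.** Inputs: 60 per arm, SD 27 at both visits, ρ = 0.5 (section 9.4) and, as an assumption, ρ = 0.7, since the protocol calls 0.5 conservative. The shifts of 1, 3 and 6 cm/s are assumptions. The largest equals the value that section 9.4 classes as a small MCID and serves as an upper case.

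- ρ = 0.5: residual SD 27 × √(1 − 0.25) = 23.38; SE 23.38 × √(2/60) = 4.27.
- ρ = 0.7: residual SD 27 × √(1 − 0.49) = 19.28; SE 19.28 × √(2/60) = 3.52.

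Rejection rates with no true effect, from the noncentral t with 118 df and noncentrality ρ|d| / SE:

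| Shift (cm/s) | ρ | Bias (cm/s) | Two-sided type I error |
|---|---|---|---|
| 1 | 0.5 | 0.5 | 5.15% |
| 3 | 0.5 | 1.5 | 6.40% |
| 6 | 0.5 | 3.0 | 10.72% |
| 1 | 0.7 | 0.7 | 5.45% |
| 3 | 0.7 | 2.1 | 9.10% |
| 6 | 0.7 | 4.2 | 21.95% |

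**Direction.** Section 9.2.2 declares superiority only when FeetMe minus conventional physiotherapy is significantly above zero (nominal 2.5% in that tail). For a 6 cm/s shift:

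- FeetMe baseline lower than control: false superiority is 10.3% at ρ = 0.5 and 21.9% at ρ = 0.7.
- FeetMe baseline higher than control: 0.4% and 0.1%.

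**Same shift at both visits.** The net bias is d − ρd = (1 − ρ)d, opposite in sign to the baseline-only case. Its size is 0.5, 1.5 and 3.0 cm/s at ρ = 0.5, and 0.3, 0.9 and 1.8 cm/s at ρ = 0.7.

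**The case against.** The strongest reply is that exposure is inferred. The protocol does not say that patient or assessor knows the arm when the baseline tests are run, and test set-up is referred to the Site User Manual, which is not part of the protocol. The size and the direction of any shift are also unknown. If patients pleased with a FeetMe allocation walk faster at baseline only, the superiority claim becomes conservative. The 22% combines the largest assumed shift with a correlation that is not the protocol's. Finally, open-label effort at the Week 12 walk enters at full weight whatever is done about baseline, whereas the baseline shift is damped by ρ.

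All of this limits the magnitude, and the 22% should not drive the grading. It does not remove the flaw: the order of steps is explicit, nothing in the protocol conceals the arm, and an error of unknown sign is not a safeguard.

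It is also fair that digital measurement removes rater error from the gait endpoints. It does not remove the patient's choice of pace, and it has no bearing on the scored and self-reported scales.

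Arm-specific instruction would still have to follow allocation, because the applications and user guides differ by arm (section 4.3, Appendix S). The insole instruction in section 7.3 is common to both arms and can come first.

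**Conclusion.** The concern holds and should be fixed. The protocol places open-label randomisation before every baseline assessment that feeds the Week 12 change analyses, without concealing the arm, so the equal-baseline constraint of the cLDA is not secured by randomisation.

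The order of steps is certain; the existence, size and direction of a shift are not. On the stated assumptions the effect is minor at 1 cm/s. At the protocol's own correlation it reaches a 3.0 cm/s bias and about 10.7% two-sided type I error at 6 cm/s. This is an avoidable route for bias into the primary endpoint, not proof that bias will occur.

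**What to change.** Keep the single-day visit and reorder it: consent, eligibility, common insole instruction and every assessment listed in section 7.3, then the IXRS randomisation. If randomisation must stay earlier, withhold the allocation from patient and assessor until the assessments are complete. Amend the synopsis, the Schedule of Assessments with its footnote 2, and sections 7.2.1.2 and 7.3 to match.

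Two adjustments follow.

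- **Recording application.** Section 7.3 allows either the Rehabilitation or the Evaluation application, and section 6.4.1 says velocity is calculated by the mobile application. A walk that precedes allocation cannot use an arm-dependent application. If one application is specified, use the same one in both arms at Baseline, Visit 3 and Visit 4.
- **Full Analysis Set.** The baseline gait measurement becomes a pre-randomisation condition, and the set can be all randomised patients. A patient with a failed baseline recording but a valid Week 12 walk can stay in the cLDA, which models both visits as outcomes. The rank-based fallback needs an observed baseline, so the handling of such patients there must be stated.

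The cost is text edits and a changed order within one visit. The sample size stays at 150 and no assessment is added. The downside is a few baseline tests in patients who are then not randomised. Open-label effort at Week 12 remains and is not addressed by this change.
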